6.0 OBJECTIVES AND OUTCOMES

The overall objective of this study is to obtain preliminary data about the effectiveness and implementation of a multi-component adherence support strategy for HIV treatment and prevention among pregnant and breastfeeding women.

6.1 Primary and secondary objectives

Our primary objective is:

- To obtain preliminary data about the effectiveness of a multi-component adherence support strategy to increase both ART and PrEP adherence during pregnancy and breastfeeding

Our secondary objectives are:

- To measure acceptability, feasibility, and fidelity of the separate components of the adherence support strategy in a “real world” setting
- To compare social harms between the intervention and control arms in the contexts of ART and PrEP
- To identify factors associated with successful ART and PrEP adherence among pregnant and breastfeeding women

Our exploratory objective is:

- To measure the incidence of maternal HIV infection among HIV-negative women on PrEP

6.2 Study Outcomes

6.2.1 Primary outcome for Trial 1 (ART adherence support)

For Trial 1, the primary outcome is retention in care with HIV viral suppression, defined as <40 copies/mL, at six months following study enrollment.

6.2.2 Secondary outcomes for Trial 1 (ART adherence support)

For Trial 1, secondary outcomes include:

- Retention in care with HIV viral suppression, defined as <1,000 copies/mL
- Adherence to ART as measured by self-report and pharmacy measures (e.g., pill count, medication possession ratio)
- Acceptability, feasibility, and fidelity of adherence support components (intervention arm only)
- Incidence of social harms and other adverse events (both arms)

6.2.3 Primary outcome for Trial 2 (PrEP adherence support)

For Trial 2, the primary outcome is retention in care with functional adherence to PrEP as measured categorically according to plasma and intracellular tenofovir drug concentrations at six months following study enrollment.

6.2.4 Secondary outcomes for Trial 2 (PrEP adherence support)

For Trial 2, secondary outcomes include:

- Adherence to PrEP as measured by self-report and pharmacy measures (e.g., pill count, medication possession ratio)
- Acceptability, feasibility, and fidelity of adherence support components (intervention arm only)
- Incidence of social harms and other adverse events (both arms)
- Incidence of maternal HIV infection

7.0 HYPOTHESES

The implementation of a multi-component adherence support strategy will increase retention in care with viral suppression among HIV-positive pregnant women on ART.

The implementation of a multi-component adherence support strategy will increase retention in care with functional PrEP adherence among HIV-negative pregnant women.

8.0 METHODOLOGY

8.1 Study design

We propose two parallel, pilot randomized trials to evaluate an integrated antiretroviral adherence support strategy for pregnant and breastfeeding women. In Trial 1, we evaluate the proposed multi-component intervention in the context of ART support for HIV-positive women. In Trial 2, we assess the efficacy of the same strategy applied to PrEP adherence among HIV-negative women at elevated risk for HIV acquisition. These pilot trials are designed to obtain preliminary data about the intervention's efficacy and its feasibility and implementation.

8.2 Study intervention

We propose a multi-component strategy to support both ART and PrEP adherence in the context of antenatal care settings. The principal components include:

8.2.1 Integrated Next Step Counseling

Integrated next step counseling (iNSC) is a structured, patient-centered approach informed by motivational interviewing techniques.^{71,72} The goal of iNSC is to foster an environment for joint-problem solving in order that the participant may identify their individual needs to increase or sustain sexual health through biomedical and non-biomedical approaches. iNSC frames the counselling sessions as a non-judgmental discussion to explore the facilitators and challenges to sexual health and medication adherence. Through this process the participant is able to identify needs to optimize sexual health protection and medication adherence.

Study staff will be trained to provide iNSC to participants randomized to the intervention arm. iNSC uses eight distinct stages to guide the counselor and patient through a semi-structured discussion: introduce, review, explore, tailor, identify, strategize, plan, and document. Within each, the counselor guides the patient through motivational interviewing and other patient-centered strategies. iNSC will be provided at each scheduled study visit by trained study personnel. A standard case report form is used to document steps included in the discussion, as well as important content emerging from exploration of facilitators, challenges, needs and strategies.

8.2.2 Adherence supporter training

There is a broad body of knowledge showing that peer or partner support can help to enhance adherence and retention in antenatal and HIV programs.⁴⁰ We propose an adherence supporter intervention. Participants will be asked to identify a partner, family member, or friend to whom they are willing to disclose their HIV status (for HIV-positive women) or their intent to initiate PrEP (for HIV-negative women). Participants may also select a clinic-based peer to serve in this adherence supporter role. Study staff will provide training for this adherence supporter in the month following enrollment, using materials adapted from similar interventions. A second “refresher” session will be provided the following month as well. The emphasis of these trainings will be basic HIV knowledge, importance of antiretroviral adherence, potential drug side effects, and practical strategies for supporting adherence. Based on our formative research, we believe the addition of this adherence supporter intervention to iNSC will help to reinforce behaviors discussed during patient-centered counseling.

8.2.3 Standard of care (control arm)

Participants randomized to the control arm will receive a similar level of engagement—compared to those in the intervention arm—when visiting the health facility, based on the current standard of care. This will include supplemental information in safe obstetrics and newborn care, based on World Health Organization and local guidelines for safe motherhood and delivered via usual practice.

8.3 Eligibility criteria

Below, we separately list the eligibility criteria for our two parallel trials. Trial 1 focuses on ART adherence support for HIV-positive pregnant women. Trial 2 focuses on PrEP adherence support for at-risk HIV-negative pregnant women. Women who have previously enrolled in the study will not be permitted to enroll again. Following informed consent, participants will be enrolled into one of two parallel randomized trials based on their HIV status.

8.3.1 Eligibility criteria for enrollment in Trial 1 (HIV-positive women)

Trial 1 inclusion criteria

- Documented pregnancy by urine pregnancy test or physical exam
- Documented positive HIV status
- Initiated on first-line ART within the past 30 days, either for the first time or after treatment interruption of 6 months or longer (if previously started but stopped ART)
- Willingness to remain in the study site's catchment area over the course of study follow-up and to comply with visit schedule
- Ability and willingness to provide informed consent

Trial 1 exclusion criteria

- Risk for intimate partner violence or social harms as a result of participation, in the judgement of the study personnel
- Other conditions that, in the judgment of the study personnel, would make participation in the study inappropriate

8.3.2 Eligibility criteria for enrollment in Trial 2 (HIV-negative women)

Trial 2 inclusion criteria

- Documented pregnancy by urine pregnancy test or physical exam
- Documented negative HIV status within the past three months
- Identified factor(s) for elevated risk for HIV acquisition, such as known positive or unknown partner HIV status; report of secondary sexual partners over the past 12 months; diagnosis of STI over the past 12 months; use of post-exposure prophylaxis in the past 12 months; reported use of shared injection material or equipment; and/or unspecified concern about HIV acquisition during pregnancy and breastfeeding
- Willingness to initiate and continue PrEP over the course of study follow-up

- Willingness to remain in the study site's catchment area over the course of study follow-up and to comply with visit schedule
- Ability and willingness to provide informed consent

Trial 2 exclusion criteria

- Positive HIV test at time of screening
- Positive hepatitis B surface antigen test at time of screening
- Renal insufficiency, defined as creatinine clearance <90 mL/min, history of known renal parenchymal disease, or known single kidney at time of screening
- Risk for intimate partner violence or social harms as a result of participation, in the judgement of the study personnel
- Other conditions that, in the judgment of the study personnel, would make participation in the study inappropriate

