8.5 Recruitment and enrollment procedures

Staff will provide interested participants with additional information and referral to the study. Potential participants will be identified at any point in their pregnancy. All women attending the ANC clinic at enrolling study facilities who meet the eligibility criteria (section 8.3) will be invited to participate in the study. All participants will undergo an informed consent procedure to ensure they are well-informed about the study, its objectives, and its requirements (section 9.2)

8.5.1 Enrollment procedures for Trial 1

Following informed consent, HIV-positive pregnant women eligible for Trial 1 will be enrolled at the same visit. We will collect social, demographic, medical, and behavioral information from all participants. We will obtain from the locator information from the participant, including phone numbers, addresses, and directions. Participants will be randomly assigned to one of two study arms (control or intervention). Statistical software will be used to generate a list of random assignments with a 1:1 ratio, balanced for each site. The randomly generated numbers will be placed in opaque sealed envelopes and sequentially numbered with participant identification numbers.⁷³

8.5.2 Enrollment procedures for Trial 2

Following informed consent, HIV-negative pregnant women eligible for Trial 2 will first undergo screening for HIV and hepatitis B surface antigen (HBsAg). Specimens will be drawn; participants will be asked to return in 1-2 weeks to confirm their eligibility to initiate PrEP. During that return visit, candidates who remain eligible (i.e., do

not meet any exclusion criteria) will be formally enrolled at this visit. Similar to Trial 1, we will then collect social, demographic, medical, and behavioral information from all participants. We will obtain locator information from the participant, including phone numbers, addresses, and directions. Participants will be randomly assigned to one of two study arms (control or intervention). Statistical software will be used to generate a list of random assignments with a 1:1 ratio, balanced for each site. The randomly generated numbers will be placed in opaque sealed envelopes and sequentially numbered with participant identification numbers.⁷³

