8.8 Study drug

8.8.1 Study drug for Trial 1

In accordance to the eligibility criteria, all HIV-positive participants in Trial 1 will be on first-line ART according to local HIV guidelines. Dispensation of ART will be managed by the local PMTCT/ART program at the study facility. We will collect information about prescribed ART drugs, pharmacy dispensations, and adherence evaluations at short visits on a monthly basis, timed with routine clinic visits.

8.8.2 Study drug for Trial 2

To ensure a consistent medication supply over the 6-month follow-up period, we will provide TDF-FTC for PrEP to all study participants in Trial 2. Packaged product will be dispensed by an on-site study staff. Participants will begin daily administration of TDF-FTC from the day of randomization to 6 months after randomization. The drug will be dispensed on a monthly basis.

Tenofovir disoproxil fumarate (TDF) and emtricitabine (FTC) are antiretroviral agents, indicated and used in combination to reduce the risk of sexually acquired HIV in adults at high risk. Each dose contains 300 mg of TDF and 200 mg of FTC, to be dosed on a daily basis.

TDF is a fumaric acid salt of the bis-isopropoxycarbonyloxymethyl ester derivative of tenofovir. The chemical name is 9-[(R)-2 [[bis[[isopropoxycarbonyl]oxy] methoxy]phosphinyl]methoxy]propyl]adenine fumarate (1:1). It has a molecular formula of C₁₉H₃₀N₅O₁₀P • C₄H₄O₄ and a molecular weight of 635.52. TDF is an acyclic nucleoside phosphonate diester analog of adenosine monophosphate. TDF requires initial diester hydrolysis for conversion to tenofovir and subsequent phosphorylations by cellular enzymes to form tenofovir diphosphate. Tenofovir diphosphate inhibits the activity of HIV-1 RT by competing with the natural substrate deoxyadenosine 5'-triphosphate and, after incorporation into DNA, by DNA chain termination. Tenofovir diphosphate is a weak inhibitor of mammalian DNA polymerases α , β , and mitochondrial DNA polymerase γ .

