8.11 Biological specimen collection and testing

All samples will be obtained from study participants by trained study staff according to approved standard operating procedures. All samples will be processed according to the assay manufacturers' specifications. Some specimens collected from patients in this protocol will be analyzed immediately per standard antenatal care guidelines. Others will be transported, processed, and temporarily housed at the University Teaching Hospital (Lusaka, Zambia) and the UNC Project Malawi (Lilongwe, Malawi). Use of stored specimens for testing that is not specifically designated in this protocol will require additional regulatory approval. All laboratory testing will be performed by trained staff using standard operating procedures and according to specific assay manufacturers' specifications.

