APPENDIX 1:

Schedule of evaluations for Trial 1 – adherence support for ART

	Clinic visits				Pharmacy visit	Pregnancy outcome
	Enrollment	Month 1	Month 3	Month 6	Monthly	6 weeks postpartum
Laboratory studies						
HIV RNA (viral load)	6 mL		6 mL	6 mL		
Hemoglobin	2 mL					
Syphilis screening	2 mL*					
Urine dipstick	X		X	X		
Vaginal microbiome	X	X				
Storage for HIV resistance testing	6 mL**			6 mL **		
Medical exam						
Medical history	X					
Obstetric exam	X	X	X	X		
Questionnaires						
Demographic information	X					
Sexual history	X			X		
Partner information	X		X	X		
Social harms (including IPV)	X	X	X	X		
Stigma	X			X		
Self-efficacy	X			X		
Depression	X			X		
HIV risk behaviors	X	X	X	X		
Delivery information						X
Study drug						
ART dispensed at PMTCT clinic					X	
Pill counts					X	
Self-report adherence					X	
Intervention assessment (Intervention arm only)						
Integrated next step counseling (iNSC)	X	X	X	X		
Adherence supporter	X					
Qualitative interviews (subset)	X***		X***	X***		

* will perform test if no results available in the medical record

** storage of leftover specimen for HIV resistance testing

*** schedule additional procedures within 30 days of visit for subset of participants enrolled in this component

Schedule of evaluations for Trial 2 – adherence support for PrEP

	Screening	Clinical visits			Pharmacy visit	Pregnancy outcome	HIV confirmatory testing
		Enrollment	Month 1	Month 3	Month 6	Monthly	6 weeks postpartum
Laboratory studies							
Rapid HIV antibody test	X	X		X	X		
Hepatitis B Antigen	4 mL						
ALT		2 mL					
Creatinine		2 mL		2 mL	2mL		
Syphilis screening		2mL *					
Urine dipstick		X	X	X	X		
Tenofovir concentration				4 mL	4 mL		
Vaginal microbiome		X	X				
HIV RNA (viral load)							4 mL
Storage for HIV resistance testing							6 mL
Medical exam							
Medical history	X						
Obstetric exam	X	X	X	X	X		
Questionnaires							
Demographic information		X					
Sexual history		X				X	
Partner information		X		X	X		
Social harms (including IPV)		X	X	X	X		
Stigma		X				X	
Self-efficacy		X				X	
Depression		X				X	
HIV risk behaviors		X	X	X	X		
Delivery information							X
Drug dispensation and adherence assessment							
PrEP dispensation						X	
Pill counts						X	
Self-report adherence						X	
Intervention assessment (intervention arm only)							
Integrated next step counseling (iNSC)		X	X	X	X		
Adherence supporter		X					
Qualitative interviews		X***		X***	X***		

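### Trial 2 excludes creatinine clearance <90 mL/min but first draws creatinine at Enrollment, when women are randomised and start TDF-FTC, and it does not require a same-day result

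*Combined protocol and SAP*

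**What the plan says.** Section 8.3.2 contains three exclusions that need a laboratory result: HIV, HBsAg and renal function. The renal one reads "Renal insufficiency, defined as creatinine clearance <90 mL/min, history of known renal parenchymal disease, or known single kidney at time of screening".

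Section 8.5.2 names the screening tests: "HIV-negative pregnant women eligible for Trial 2 will first undergo screening for HIV and hepatitis B surface antigen (HBsAg". It continues: "Specimens will be drawn; participants will be asked to return in 1-2 weeks to confirm their eligibility to initiate PrEP". At the return visit, candidates who do "not meet any exclusion criteria) will be formally enrolled at this visit". Baseline data collection and randomisation follow.

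Section 8.8.2 fixes the start of drug: "Participants will begin daily administration of TDF-FTC from the day of randomization to 6 months after randomization".

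In the Trial 2 schedule in Appendix 1, the row "Rapid HIV antibody test" is marked at both Screening and Enrollment, and HBsAg has 4 mL at Screening. The creatinine row is empty at Screening and has 2 mL at Enrollment, Month 3 and Month 6.

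On laboratory handling, section 8.11 says: "Some specimens collected from patients in this protocol will be analyzed immediately per standard antenatal care guidelines". It then says: "Others will be transported, processed, and temporarily housed at" two named laboratories. It does not say which route creatinine takes.

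**The concern.** The screening phase exists so that eligibility can be settled before a woman is enrolled. It covers two of the three laboratory exclusions. The third rests on a specimen first taken at the visit where the decision is made, with the drug starting from that day.

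If the result is not back the same day, the text leaves staff two courses. They can send the woman home and enrol her later, which adds a visit that the plan does not foresee. Or they can treat an unknown clearance as not excluded and dispense. Under the second course, a pregnant woman whom the sponsor meant to exclude could take TDF-FTC until the result arrives. What is at stake is safety and correct application of an eligibility criterion.

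**Working it through.** The plan states no figure to reproduce on this point. The check sets the sections against each other, with a short sum for blood volume.

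**1. Each laboratory exclusion against its first scheduled test**

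| Exclusion (8.3.2) | Named as a screening test in 8.5.2 | First test in Appendix 1 |
|---|---|---|
| HIV | Yes | Screening |
| HBsAg | Yes | Screening |
| Creatinine clearance | No | Enrollment |

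So 2 of 3 have a screening test.

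**2. Is the creatinine row read correctly?** Some Trial 2 rows look shifted in the extracted table, for example sexual history and HIV RNA, so the row was checked against its neighbours. HBsAg and the rapid HIV test fill the first column (Screening). Dipstick runs through columns two to five (Enrollment, Months 1, 3 and 6). Tenofovir concentration fills columns four and five (Months 3 and 6). Creatinine fills columns two, four and five, which on the same pattern are Enrollment, Month 3 and Month 6. Section 8.5.2 independently names only HIV and HBsAg for screening.

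**3. Order of events.** Screening with HIV and HBsAg; an interval of 1-2 weeks; the Enrollment visit with the first creatinine draw, confirmation of eligibility and randomisation; TDF-FTC from that day. The documents do not mention a creatinine draw at screening, a required same-day assay, use of a value already on file, or a hold on randomisation or dispensing until the result is known.

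**4. What else would identify a woman below the threshold?**
- Medical history at Screening finds kidney disease or a single kidney that is already known.
- Dipstick at Enrollment and Months 1, 3 and 6 gives no clearance value.
- Review of adverse events at study visits (8.10) and creatinine at Months 3 and 6 act after drug has started.

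None of these supplies the clearance before the first dose.

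**5. Blood volume if the draw moves** (volumes from Appendix 1; the syphilis test is done only if no result is on record)
- Now: Screening 4 (HBsAg) = 4 mL; Enrollment 2 (ALT) + 2 (creatinine) + 2 (syphilis) = 6 mL; sum 4 + 6 = 10 mL. Without syphilis: 4 + 4 = 8 mL.
- After the move: Screening 4 + 2 = 6 mL; Enrollment 2 + 2 = 4 mL; sum 6 + 4 = 10 mL. Without syphilis: 6 + 2 = 8 mL.
- Months 3 and 6 each add creatinine 2 + tenofovir 4 = 6 mL, or 12 mL together. The listed total over scheduled visits is therefore 10 + 12 = 22 mL (8 + 12 = 20 mL without syphilis), before and after the move.

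**The case against.** The strongest reply is that the safeguard is already written. Section 8.5.2 makes the return visit the point at which eligibility is confirmed, and it enrols only women who meet no exclusion criterion. The schedule names a visit, not an order within it, so a creatinine drawn early in the Enrollment visit could inform the decision if the assay is fast. Section 8.11 allows for immediate analysis of some specimens. Sections 8.11 and 8.12 refer to laboratory SOPs, which are not in the documents and may specify the turnaround. This stands to the following extent: the text does not show that the draw comes after randomisation, and it does not show that sites lack a same-day result. It also does not require one, and the eligibility check cannot act on a value that nobody yet has.

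A second reply is that the words about the time of screening may attach only to the single kidney. On that reading the mismatch of wording disappears. Clearance is still an exclusion to be settled before enrolment, and it is still first measured at the same visit.

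A third reply is that harm needs three things together: no same-day result, staff who proceed without it, and a woman who is in fact below 90 mL/min. That is fair. None of the three is evidenced, and the alternative course of postponing enrolment exposes nobody to drug.

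Finally, moving the draw is not free. The baseline creatinine used as comparator for Months 3 and 6 would then be taken 1-2 weeks before drug start. That is a reason to offer a second option, not a reason to leave the text as it is.

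**Conclusion.** The point holds as a gap in procedure. One of three laboratory exclusions has no screening test, and the eligibility check that depends on it works only with a same-day result that the plan does not require. It should be fixed because the remedy is small and the drug is given to pregnant women, but it is not a fatal flaw.

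The schedule governs the baseline creatinine of all 200 planned Trial 2 women (100 per arm). A reader might infer that all 200 are at risk, or that women below the threshold will be enrolled and dosed. The documents do not support either: 8.5.2 bars any woman known to meet an exclusion, and neither the proportion below 90 mL/min nor the laboratory turnaround is given. No number of exposed women can be stated. A reader might also infer an effect on power or on the comparison of arms. Nothing in the documents supports that, and none is claimed.

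The conclusion rests on the column reading set out above, which agrees with the text of 8.5.2, and on the protocol as written, without the SOPs.

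**What to change.** Preferred: in the Trial 2 schedule in Appendix 1, move the baseline 2 mL creatinine draw from Enrollment to Screening, and name it in 8.5.2 beside HIV and HBsAg. The result can then be in hand at the 1-2 week return visit.

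Alternative: keep the draw at Enrollment and state in 8.5.2 that a same-day creatinine result must be reviewed before randomisation and first dispensing. The reference to screening time in 8.3.2 should then be aligned with that. The choice belongs to the sponsor's clinicians.

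The cost of the preferred change is one cell and one sentence. A screening blood draw already exists for HBsAg, so no extra venepuncture is needed, and the volume for an enrolled woman does not change. There are two downsides: one 2 mL creatinine test for each woman who is screened but not enrolled, and a baseline value that predates drug start by 1-2 weeks. The alternative avoids both but depends on each site being able to return a result within the visit.
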